4.4.1 Clinical Criteria for Early Study Termination

There are no pre-specified criteria for terminating the trial early.

A primary objective of this early Phase I trial is to identify a safe and well-tolerated dose and/or dosing regimen that achieve pharmacokinetic, pharmacodynamic and/or biologic targets in humans based on preclinical or early clinical data. Therefore, it is possible that trial participants may not receive all doses specified in the protocol if this objective is achieved at lesser dose levels in this trial. This would not be defined as early termination of the trial, but rather an earlier than anticipated achievement of the trial objective(s). If a finding (e.g., pharmacokinetic, pharmacodynamic, efficacy, biologic targets, etc.) from another preclinical or clinical trial using the trial treatment(s), comparator(s), drug(s) of the same class, or methodology(ies) used in this trial, results in the trial(s) or program being

stopped for non-safety reasons, this also does not meet the definition of early trial termination.

Early trial termination is defined as a permanent discontinuation of the trial due to unanticipated concerns of safety to the trial participants arising from clinical or preclinical trials with the trial treatment(s), comparator(s), drug(s) of the same class or methodology(ies) used in this trial.

The clinical study may be terminated early if the extent (incidence and/or severity) of emerging effects is such that the risk/benefit ratio to the study population as a whole is unacceptable. In addition, further recruitment in the study or at a particular study site(s) may be stopped due to insufficient compliance with the protocol, GCP, and/or other applicable regulatory requirements, procedure-related problems or the number of discontinuations for administrative reasons is too high.

5 STUDY POPULATION

Male and Female of non-child bearing potential (WONCBP) participants with ESRD on HD between the ages of 18 and 80 years (ages ≥ 40 and ≤ 80 for Part 1 and ≥ 18 and ≤ 80 for Part 2) will be enrolled in this study.

Prospective approval of protocol deviations to recruitment and enrollment criteria, also known as protocol waivers or exemptions, is not permitted.

5.1 Inclusion Criteria

A participant will be eligible for inclusion in the study if the participant:

Type of Participant and Disease Characteristics

1. ESRD maintained on stable outpatient HD regimen, using an established (>3 months) and normally functioning, regular flow, uninjected mature AV fistula or AV graft and skin consistent with standard chronic HD access injuries, and HD stability defined as $Kt/V \geq 1.2$ within 3 months prior to dosing at a healthcare center for > 3 month from dosing.
2. On HD regimen at least 3 times per week for a minimum of 3 hours per dialysis session, using a complication-free well-maintained AV fistula or AV graft, expected and plan to continue this throughout and for at least 3 months beyond the study.
3. Have a Body Mass Index (BMI) ≥ 18 and $\leq 45 \text{ kg/m}^2$. BMI = weight (kg)/height (m) 2 .
4. Baseline health is judged to be stable based on medical history, physical examination, vital sign measurements and ECG performed prior to randomization.

5. Liver function test (serum alanine aminotransferase [ALT] and aspartate aminotransferase [AST]) must be equal to or below 1.5X upper limit of normal (ULN) and deemed not clinically significant by both the investigator and the Sponsor.
6. Be willing to comply with the trial restrictions (see Section 5.3) for a complete summary of trial restrictions).

Demographics

7. Be male or female, of non-child bearing potential (WONCBP) from 40 years to 80 years of age inclusive for Part 1, and 18 years to 80 years of age inclusive for Part 2, at the time of signing the informed consent.

Male Participants

Contraceptive use by men should be consistent with local regulations regarding the methods of contraception for those participating in clinical studies.

8. Agree to use a male condom plus partner use of an additional contraceptive method when having penile-vaginal intercourse with a WOCBP who is not currently pregnant. Note: Men with a pregnant or breastfeeding partner must agree to remain abstinent from penile-vaginal intercourse or use a male condom during each episode of penile-vaginal penetration.

Female Participants

Contraceptive use by women should be consistent with local regulations regarding the methods of contraception for those participating in clinical studies.

9. A female participant is eligible to participate if she is not pregnant or breastfeeding, and one of the following conditions applies:
 - a. She is not a woman of childbearing potential (WOCBP), satisfying one of the two criteria below:
 - i. If the participant is a postmenopausal female: she is without menses for at least 1 year and has a follicle stimulating hormone (FSH) value in the postmenopausal range upon pre-study (screening) evaluation.
 - ii. If the participant is a surgically sterile female: she is status post hysterectomy, bilateral salpingectomy, oophorectomy or tubal ligation. NOTE: These procedures must be confirmed with medical records. In the absence of documentation, hysterectomy may be confirmed by pelvic exam or if necessary by ultrasound; oophorectomy may be confirmed by hormone levels, particularly follicle stimulating hormone (FSH) in the post-menopausal range, but tubal ligation without records

should be excluded. Information must be captured appropriately within the site's source documents.

Informed Consent

10. The participant (or legally acceptable representative) has provided documented informed consent/assent for the study. The participant may also provide consent/assent for FBR. However, the participant may participate in the study without participating in FBR.

Additional Categories

Consent must be documented by the participant's dated signature or by the participant's legally acceptable representative's dated signature on a consent form along with the dated signature of the person conducting the consent discussion.

A copy of the signed and dated consent form should be given to the participant before participation in the trial.

The initial informed consent form, any subsequent revised written informed consent form and any written information provided to the participant must receive the IRB/ERC's approval/favorable opinion in advance of use. The subject or his/her legally acceptable representative should be informed in a timely manner if new information becomes available that may be relevant to the participant's willingness to continue participation in the trial. The communication of this information will be provided and documented via a revised consent form or addendum to the original consent form that captures the subject's dated signature or by the participant's legally acceptable representative's dated signature.

Specifics about a trial and the trial population will be added to the consent form template at the protocol level.

The informed consent will adhere to IRB/IEC requirements, applicable laws and regulations and Sponsor requirements.

5.2 Exclusion Criteria

The participant must be excluded from the study if the participant:

Medical Conditions

1. Has a history of any clinically significant concomitant disease or condition (including treatment for such conditions) or diseases whose current condition is considered clinically unstable that, in the opinion of the investigator, could either interfere with the study drug, compromise interpretation of study data, or pose an unacceptable risk to the patient. Participants with a remote history of uncomplicated medical events (e.g., uncomplicated kidney stones, as defined as spontaneous passage and no recurrence in the last 5 years, or childhood asthma) may be enrolled in the study at the discretion of the investigator.

2. Is mentally or legally incapacitated, has significant emotional problems at the time of pre-study (screening) visit or expected during the conduct of the study or has a history of clinically significant psychiatric disorder of the last 5 years. Participants who have had situational depression may be enrolled in the study at the discretion of the investigator.
3. Has a history of cancer (malignancy), including adenocarcinoma,

Exceptions: (1) Subjects with adequately treated non-melanomatous skin carcinoma may participate in the trial; (2) Subjects with other malignancies which have been successfully treated ≥ 10 years prior to the pretrial (screening) visit where, in the judgment of both the investigator and treating physician, appropriate follow-up has revealed no evidence of recurrence from the time of treatment through the time of the pretrial (screening) visit (except those cancers identified at the beginning of exclusion criterion 10); or, (3) Subjects, who, in the opinion of the trial investigator, are highly unlikely to sustain a recurrence for the duration of the trial.

4. Has blood coagulation test (aPTT, PT) $\geq 20\%$ outside of normal range on pretrial (screening), which are considered clinically significant by both the investigator and the sponsor.
5. Any other clinically significant abnormalities in laboratory test results at screening that would, in the opinion of the investigator, increase the patient's risk of participation, jeopardize complete participation in the study, or compromise interpretation of study data.
6. Has a history of deep vein thrombosis or pulmonary embolism. Has a history of vascular access thrombosis within 1 month prior to enrollment. Has a personal or family history of bleeding disorder (e.g., hemophilia, Factor V Leiden, prothrombin gene mutation, protein C or S deficiency, ATIII deficiency, anti- phospholipid Ab syndrome).
7. Has a history of GI bleeding, duodenal polyps or gastric ulcer in the last 5 years or severe hemorrhoidal bleed in last 3 months.
8. Has a history of or current frequent epistaxis within the last 3 months or active gingivitis.
9. Has ongoing anticoagulant therapy (warfarin, apixaban, dabigatran, rivaroxaban, edoxaban, betrixaban) or antiplatelet therapy (clopidogrel, prasugrel, ticagrelor, ticlopidine). Intradialytic heparin and aspirin are permitted.
10. At the time of screening or pre-dose, has planned significant dental procedures (including planned dental surgery), or other planned surgical procedures within duration of participation in the trial.
11. Is positive for hepatitis B surface antigen or HIV. Participants positive for hepatitis C antibodies may be enrolled with agreement of both investigator and sponsor.

12. Had major surgery, donated or lost 1 unit of blood (approximately 500 mL) within 4 weeks prior to the pre-study (screening) visits.
13. Has a history of significant multiple and/or severe allergies (e.g. food, drug, latex allergy), or has had an anaphylactic reaction or significant intolerance (i.e. systemic allergic reaction) to prescription or non-prescription drugs or food.
14. Has a tattoo, scar, or other physical finding at the area of the infusion site that would interfere with infusion or a local tolerability assessment.
15. Has a history (subject recall) of receiving any human immunoglobulin preparation such as IVIG or RhoGAM within the last year.
16. Has a history (subject recall) of receiving any biological therapy (including human blood products or monoclonal antibodies; excluding erythropoietin and insulin) within the last 3 months or 5 half-lives (whichever is longer), or vaccination within the last 1 month.

Exceptions:

- Participants who have received seasonal flu vaccine and pneumococcal vaccine within the last 1 month may be enrolled at the discretion of the investigator.
- COVID-19 vaccine may be administered. Study intervention must be given at least 72 hours following or at least 48 hours prior to any COVID-19 vaccination. Investigational COVID-19 vaccines (i.e., those not licensed or approved for Emergency Use) are not allowed.

17. Exclusion criteria for ECG:

- Heart rate < 40 or > 110 bpm
- QTc interval > 500 msec
- Any significant arrhythmia or conduction abnormality, (including but not specific to atrioventricular block [2nd degree or higher], Wolff Parkinson White syndrome [unless curative radio ablation therapy]), which, in the opinion of the investigator and sponsor, could interfere with the safety for the individual patient.
- Non-sustained or sustained ventricular tachycardia (> 2 consecutive ventricular ectopic beats at a rate of > 1.7/second).

Prior/Concomitant Therapy

18. Is unable to refrain from or anticipates the use of medication, including prescription and nonprescription drugs or herbal remedies beginning approximately 2 weeks (or 5 half-lives) prior to administration of the initial dose of study drug, throughout the study until

the poststudy visit. Allowed and prohibited concomitant meds are discussed in Section 6.5.

Prior/Concurrent Clinical Study Experience

19. Has participated in another investigational study within 4 weeks (or 5 half-lives, whichever is greater) prior to sponsor's investigational drug (MK2060/placebo) administration. The window will be derived from the date of the last dose in the previous study.

Diagnostic Assessments

20. Has a blood pressure >190 mmHg systolic or >110 mmHg diastolic.

Other Exclusions

21. Is under the age of legal consent.
22. Consumes greater than 3 glasses of alcoholic beverages (1 glass is approximately equivalent to: beer 354 mL/12 ounces, wine 118 mL/4 ounces, or distilled spirits 29.5 mL/1 ounce) per day. Participants who consume 4 glasses of alcoholic beverages per day may be enrolled at the discretion of the investigator.
23. Consumes excessive amounts, defined as greater than 6 servings (1 serving is approximately equivalent to 120 mg of caffeine) of coffee, tea, cola, energy drinks, or other caffeinated beverages per day.
24. Is a regular user of any illicit drugs or has a history of drug (including alcohol) abuse within approximately 2 years. Participants must have a negative serum or saliva drug screen prior to randomization. Participants with a positive drug screen due to the use of physician prescribed medications (e.g., opioids, benzodiazepines, antidepressants) may be enrolled at the discretion of the investigator. In addition, participants with a positive THC may be enrolled at the discretion of the investigator if the participants' THC use is under 4 times/month and the participants agree to not use during their study participation. Participants with positive THC on screening may have rechecks performed at the discretion of the investigator to ensure compliance with abstinence from THC use during study participation.
25. Presents any concern by the investigator regarding safe participation in the study or for any other reason the investigator considers the participant inappropriate for participation in the study.
26. Is or has an immediate family member (eg, spouse, parent/legal guardian, sibling, or child) who is investigational site or Sponsor staff directly involved with this study.

5.3 Lifestyle Considerations

5.3.1 Meals and Dietary Restrictions

Fasting requirements for trial procedures, such as, but not limited to, laboratory safety evaluations are specified in Section 8.

All meals on study dosing days will be served as to not interfere with the study procedures.

On dosing days, subjects will fast from all food and drinks, except water, for at least 8 hours prior to study drug administration. Subjects will continue to fast until 2 hours after study drug administration when they will be given a light breakfast. A lunch and dinner will be provided at time points indicated in the trial flowchart. Additional meals and snack(s) will be provided by the investigator as per the CRUs standard procedures. Subjects will fast from all food and drinks except water between meals and snacks. After 24-hour post-dose procedures on dosing days have been completed, subsequent meals and snacks will be unrestricted in caloric content, composition and timing.

Instructions on whether to take MK-2060 with or without food and/or drink may be modified during the trial based on newly available data.

5.3.2 Caffeine, Alcohol, and Tobacco Restrictions

5.3.2.1 Caffeine Restrictions

Participants will refrain from consumption of caffeinated beverages and xanthine-containing products from 12 hours prior to the pre- and post-trial visits, from 12 hours prior to and 12 hours after study drug administration, and 12 hours prior to scheduled outpatient visits. At all other times, caffeinated beverages or xanthine-containing products will be limited to no more than 6 units per day amounts (>6 units: 1 unit=120 mg of caffeine).

5.3.2.2 Alcohol Restrictions

Participants will refrain from consumption of alcohol 24 hours prior to the pre- and post-trial visits, from 24 hours prior to and after study drug administration.

Participants will refrain from consumption of alcohol 12 hours prior to scheduled outpatient visits.

At all other times, alcohol consumption is limited to no more than approximately 3 alcoholic beverages or equivalent (1 glass is approximately equivalent to: beer [~355 mL/12 ounces], wine [~118 mL/4 ounces], or distilled spirits [~29.5 mL/1 ounce]) per day.

5.3.2.3 Tobacco Restrictions

Smoking (and/or the use of nicotine/nicotine-containing products) is permitted during the study. Participant should follow CRU's smoking restrictions during domiciling.

5.3.3 Activity Restrictions

Participants will avoid unaccustomed strenuous physical activity (ie, weight lifting, running, bicycling, etc.) from the pre-study (screening) visit until administration of the initial dose of study drug, throughout the study and until the poststudy visit.

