2.2.2 Ongoing Clinical Studies

Protocol 001

Protocol MK-2060-001 is a double-blind, randomized, placebo-controlled, single site, sequential panel study to evaluate the safety, tolerability, PK, and PD of single ascending dose administration of SC and IV doses of MK-2060 in healthy male participants. The clinical conduct of PN001 is complete. 36 healthy male participants received single SC doses of MK-2060 up to 120 mg and 24 healthy male subjects received single IV doses of MK-2060 up to 40 mg. MK-2060 was generally well-tolerated and there were no SAEs or discontinuations due to AEs. Refer to the IB Edition 4 for a detailed overview of the study, and available preliminary PK, PD, and safety results.

Protocol 004 Part 1 Panels A, B and C:

As of 09-Oct-2020, 24 participants have been administered one IV dose up to 40 mg MK-2060 or placebo. To date, single IV doses up to 40 mg have been generally well tolerated and there have been no treatment emergent SAEs and no discontinuations due to any drug-related AEs. There have been no AEs suggestive of hypersensitivity. Refer to IB Edition 4 for a detailed overview of preliminary safety, PK and PD results for Part 1 Panels A, B and C.

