Part 2: Part 2 will be the first study of multiple dosing of MK-2060 in older adult patients with ESRD on HD. In this part, approximately 20 participants will be randomized to a 3 times per week for the 1st week and then once weekly dose for 3 weeks of MK-2060 or placebo (0.9% sodium chloride infusion, USP sterile saline) in a treatment ratio of 3:1 (15 active and 5 placebo) for total of 4 weeks of dosing. Participants will receive a loading dose up to 25 mg IV MK-2060 or placebo for a total of 3 doses in week 1 and a weekly maintenance dose up to 25 mg IV MK-2060 or placebo in weeks 2-4. Participants will not be dosed until 14 days of safety data and available PK data from at least 6 participants in the 40mg IV panel (Part 1 Panel C) of this trial has been reviewed. Participants who have completed Part 1 Panel A, B, or C may be enrolled in Part 2 of the study with joint agreement of the Investigator and the Sponsor.

Participants will be domiciled for the 1st week until ~ 24 hours post the third dose and for ~24 hours after each study drug administration in weeks 2-4 for safety/tolerability monitoring. Participants may be domiciled longer pending the investigator requirements and/or the preference of the participant. Participants will be closely monitored for safety and tolerability, including safety labs, local lab aPTT and PT results, physical exam to check incidence of bleeding, vital signs (VS) and 12-lead ECG, as well as local infusion site reactions and for systemic reactions to infusion. All participants in this study will be followed through approximately 3 months after the last study dose (Dose #6) for safety and tolerability, including all adverse experiences, safety labs, local lab aPTT and PT results, physical exam to check incidence of bleeding, vital signs (VS) and 12-lead ECG.

The trial design is depicted in [Figure 1, Figure 2 and Table 1]. For all panels in Part 1 and Part 2, participants will be followed for approximately 164 days or 90 days post the last dose of study drug respectively. Blood samples will be collected for MK-2060 plasma PK and PD to assess aPTT/PT levels, fibrin generation, and FXI activity levels.

The precise timing of safety and tolerability measurements, PK and PD samples may be altered during the course of the study based on newly available data (i.e., to obtain data closer to the time of peak concentrations or to better describe the half-life of the compound).

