In Part 2 (multiple dose), in order to mimic the therapeutic setting, 3 doses given on Days 1, 3, and 5 will be studied in addition to the weekly maintenance dose. A weekly maintenance dosing frequency was selected to reduce the peak to trough ratio without posing a significant burden to ESRD patients who undergo dialysis 3 times a week and can receive an IV infusion concurrent with dialysis. A less frequent dosing interval would result in higher peak concentrations and patients being sustained at maximal FXI inhibition levels longer, which could potentially increase bleeding risk in this vulnerable population. For anticoagulants, it is desirable to achieve near target anticoagulation as soon as therapy is initiated. Given the half-life of ~18 days observed in Part 1 of PN004 and the dosing frequency of QW, without the 3 doses given during week 1 (loading dose) it would take weeks to achieve steady state exposure and target anticoagulation. Thus, the 3 doses during week 1 are introduced to help achieve desired anticoagulation immediately after initiation of therapy.

Participants will be discharged following the ~52- or ~24-hour (24 hours after last dose for Week 1 and 24 hours after each dose in Weeks 2-4) in-clinic period after dosing for Part 1 or Part 2 accordingly, but they will continue to be monitored throughout the trial period and return to the site post-dose as specified in the SoA (safety evaluations as indicated in the flow chart (including repeat physical examinations, infusion reaction assessments, laboratory safety assessments, hemoccult, local lab aPTT and PT tests).

Following discharge, the following measures are being taken in this protocol to ensure the safety of study participants:

- Participants will be informed that they could be taking an anticoagulant as a participant in this trial, and that this might increase the risk of bleeding as might occur in surgery, dental procedures, or strenuous exercise/contact sport activities.
- Participants will be excluded if they have planned significant dental procedures, including surgery, or other planned surgical procedures within duration of participation in the trial.

- Participants will be required to avoid scheduling any surgical or dental procedures, and to avoid strenuous physical activity and contact sport activities for the duration of the trial.

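### Section 5.3.3 restricts only unaccustomed strenuous activity and leaves out contact sport, which is narrower than the bleeding safeguard in Section 4.3.5

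*Combined protocol and SAP*

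**What the plan says.** Section 5.3.3 (Activity Restrictions) is the only activity rule in Section 5.3: "Participants will avoid unaccustomed strenuous physical activity (ie, weight lifting, running, bicycling, etc". It applies "from the pre-study (screening) visit until administration of the initial dose of study drug, throughout the study and until the poststudy visit". Contact sport is not mentioned there or elsewhere in Section 5.3.

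Section 4.3.5 lists measures taken after discharge for participant safety. One is that participants must "avoid strenuous physical activity and contact sport activities for the duration of the trial". The same list gives the reason: participants are told they could be receiving an anticoagulant and that "this might increase the risk of bleeding as might occur in surgery, dental procedures, or strenuous exercise/contact sport activities".

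Inclusion criterion 6 (Section 5.1) ties eligibility to the restrictions and points to one place for them: "Be willing to comply with the trial restrictions (see Section 5.3) for a complete summary of trial restrictions".

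**The concern.** The two rules cover much the same period but not the same behaviour. Someone who regularly lifts weights, runs, cycles or plays a contact sport complies with 5.3.3 by carrying on, and in doing so breaches 4.3.5.

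The reason given in 4.3.5 is bleeding under a possible anticoagulant. Nothing in that reason depends on whether the participant is used to the activity, so the qualifier in 5.3.3 works against the purpose of the safeguard. A site that screens and instructs from Section 5.3, as criterion 6 invites it to, would apply a weaker rule than the one on which the protocol's risk justification relies.

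What is at stake is a participant safety instruction. No bias in any endpoint is suggested.

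**Working it through.** The protocol gives no figure on this point, so the check is a comparison of text, followed by simple arithmetic on how many people and how much time could be involved.

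**The two rules side by side**

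| | Section 5.3.3 | Section 4.3.5 |
|---|---|---|
| Strenuous activity | Barred only if unaccustomed | Barred without qualification |
| Contact sport | Not named | Named and barred |
| Period | Screening to poststudy visit | Duration of the trial (listed under post-discharge measures) |
| Pointed to by Inclusion 6 | Yes, as part of Section 5.3 | No |

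The list in 5.3.3 is open-ended, so contact sport could be read into it. The qualifier would still apply, and only unaccustomed contact sport would be caught. Both differences therefore remain on the most generous reading.

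Other measures in the 4.3.5 list do have operative counterparts. Planned procedures are covered by Exclusion 10, the identification card by Section 8.1.3, the bracelet by the schedules of activities, and the aPTT/PT retention rule by Section 8.1.11. The activity rule is the one that loses content on the way.

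**Who could be affected**

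- Part 1: by 09-Oct-2020, "24 participants have been administered one IV dose up to 40 mg MK-2060 or placebo" (Section 2.2.2), which is the full Part 1 complement of 24. The practical reach is therefore mainly Part 2.
- Part 2: about 20 participants, 15 active and 5 placebo (Section 4.1), aged 18 to 80.
- Share already accustomed to such activity: not given. Assumed range 0 to 10%.
- All Part 2: 20 × 0 = 0 to 20 × 0.10 = 2.
- Active arm: 15 × 0 = 0 to 15 × 0.10 = 1.5.

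**For how long**

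- Participants are "domiciled for the 1st week until ~ 24 hours post the third dose" (Section 4.1). The third dose is on Day 5, so first discharge is about Day 6.
- The poststudy visit is Day 111. Window: 111 − 6 = 105 days, less three stays of about 24 hours after the Day 8, 15 and 22 doses.

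**How much drug is present**

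Section 4.3.5 supplies the half-life: "Given the half-life of ~18 days observed in Part 1 of PN004". Taking simple exponential decline after the last dose on Day 22:

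- Day 58: 36 / 18 = 2 half-lives, 25% remaining.
- Day 76: 54 / 18 = 3 half-lives, 12.5% remaining.
- Day 111: 89 / 18 = 4.94 half-lives, 2^(−4.94) = 0.032, about 3% remaining.

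Section 4.3.4 projects that more than 90% of participants will have aPTT at 1.5-fold baseline at trough on 25 mg weekly. That projection covers the weekly dosing phase and should not be carried into the washout.

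**The case against.** The strongest reply is that the safeguard is already in the protocol. Section 4.3.5 is current and binding, anyone who follows it also satisfies 5.3.3, and so this is incomplete repetition and not a missing rule. That is true, and it limits the seriousness of the point. It does not remove the mismatch, because the eligibility criterion points to the narrower text.

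It can also be said that criterion 6 requires willingness to follow the trial restrictions, that 4.3.5 states one of them, and that the mention of Section 5.3 is only a pointer in a badly punctuated sentence. That reading is available. But the pointer calls Section 5.3 complete, and a site has no reason to search a dose-interval rationale for further participant rules.

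Third, how sites actually instruct participants is unknown. The consent documents are not available here, and 4.3.5 separately requires that participants be told about bleeding with strenuous exercise and contact sport. The card, the bracelet and investigator discretion under Exclusion 25 add further protection. These layers reduce the risk, but none of the ones visible in the protocol states the activity rule.

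Fourth, the 4.3.5 measure is listed under steps taken after discharge, so applying it from screening could bar habitual exercise for up to about 28 days before a new participant has received any drug. Since 5.3.3 already runs from screening, no new period is created, but the content during screening would become stricter. That part of the objection stands as a small cost.

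Finally, the numbers are slight: the assumed range includes nobody, and little drug remains by Day 111. Both are accepted.

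**Conclusion.** The point holds. Section 5.3.3 is narrower than 4.3.5 in two respects, the qualifier on strenuous activity and the absence of contact sport, and it sits in the section that Inclusion 6 calls complete. This is a minor inconsistency in a bleeding safeguard that should be corrected; it has no consequence for any estimate, test or stopping rule.

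The likely reach is 0 to 2 of about 20 Part 2 participants (0 to 1.5 of the 15 on active drug) over roughly 105 days, with exposure falling through the last 89. The head count rests entirely on the assumed 0 to 10% share. The finding that the two texts differ rests on no assumption.

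**What to change.** In Section 5.3.3, delete *unaccustomed* and add contact sport, so that in substance participants avoid strenuous physical activity (for example weight lifting, running, bicycling) and contact sport from the screening visit for the duration of the trial. This adopts the protocol's own stricter rule. If the sponsor sees no need for it before dosing, the stricter wording could begin at the first dose, with the present wording kept for screening.

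A cross-reference from Section 5.3 to the 4.3.5 rule on scheduling surgical or dental procedures would be a useful optional addition. Exclusion 10 needs no change.

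The cost is a few words. There is no new visit, procedure or analysis. From first discharge, habitually active participants face nothing that 4.3.5 does not already require of them.
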